6.3.2 Secondary Effectiveness Endpoint

If any item in either the full or partial Mayo score was not collected, the subject will be excluded from the relevant secondary effectiveness endpoint analysis.

(1) Percentage (%) of subjects who showed clinical remission^c at visit 2 (week 8) and who showed clinical remission^c at visit 4 (week 24) and visit 8 (week 56) among those who showed a clinical response at visit 2 (week 8)

CONFIDENTIAL:

THIS DOCUMENT AND THE INFORMATION CONTAINED HEREIN ARE PROPRIETARY TO THE COMPANY AND ARE NOT TO BE DISCLOSED WITHOUT THE WRITTEN PERMISSION OF THE COMPANY.

02-NOV-2018

Last Update Date

STATISTICAL ANALYSIS PLAN (V2.0)

The frequency and percentage of subjects who showed clinical remission^c at visit 2 (week 8) will be presented. Among the subjects who showed a clinical response at visit 2 (week 8), the frequency and percentage of those who showed clinical remission^c at visit 4 (week 24) and visit 8 (week 56) will also be presented.

^c Clinical remission: Defined as the case of full Mayo score ≤2 points and each subscore ≤1 point. For visit 4 (week 24), however, it is defined as the case of partial Mayo score ≤2 points and each subscore ≤1 point.

(2) Percentage (%) of subjects who showed a clinical response at visit 2 (week 8) without steroid administration^d, and who showed a clinical response at visit 4 (week 24) and visit 8 (week 56) without steroid administration^d among those who showed a clinical response at visit 2 (week 8)

The frequency and percentage of subjects who showed a clinical response at visit 2 (week 8) without steroid administration^d will be presented. Among these subjects, the frequency and percentage of those who showed a clinical response at visit 4 (week 24) and visit 8 (week 56) without steroid administration^d will also be presented.

^d Clinical response without steroid administration: Defined as the case where the subject showed a clinical response without using systemic steroids within 12 weeks before he/she was evaluated. For visit 2 (week 8), however, it is defined as the case where the subject showed a clinical response without using systemic steroids within 8 weeks before he/she was evaluated.

(3) Percentage (%) of subjects who showed clinical remission without steroid administration^d at visit 2 (week 8), and among the subjects who showed a clinical response at visit 2 (week 8), those who showed clinical remission without steroid administration^d at visit 4 (week 24) and visit 8 (week 56)

The frequency and percentage of subjects who showed clinical remission without steroid administration^d at visit 2 (week 8) will be presented. Among the subjects who showed a clinical response at visit 2 (week 8), the frequency and percentage of those who showed clinical remission without steroid administration^d at visit 4 (week 24) and visit 8 (week 56) will also be presented.

d Clinical remission without steroid administration: Defined as the case where the subject showed clinical remission without using systemic steroids within 12 weeks before he/she was evaluated. For visit 2 (week 8), however, it is defined as the case where the subject showed clinical remission without using systemic steroids within 8 weeks before he/she was evaluated.

| dreamcis ATIGERMED COMPANY | | Last Update Date |
|----------------------------------|---|------------------|
| | CONFIDENTIAL: | |
| | THIS DOCUMENT AND THE INFORMATION CONTAINED HEREIN ARE PROPRIETARY TO THE COMPANY AND ARE NOT TO BE DISCLOSED | 02-NOV-2018 |
| | WITHOUT THE WRITTEN PERMISSION OF THE COMPANY. | |
| STATISTICAL ANALYSIS PLAN (V2.0) | | |

(4) Percentage (%) of subjects who showed mucosal healing^e at visit 2 (week 8), and among the subjects who showed a clinical response at visit 2 (week 8), those who showed mucosal healing^e at visit 8 (week 56)

The frequency and percentage of subjects who showed mucosal healing^e at visit 2 (week 8) will be presented. Among the subjects who showed a clinical response at visit 2 (week 8), the frequency and percentage of those who showed mucosal healing^e at visit 8 (week 56) will also be presented.

^e Mucosal healing: Defined as the case of an endoscopy subscore of 0 or 1 in the full Mayo score

(5) Changes in the partial Mayo score over time from visit 1 (baseline)

[figure not shown]
For the partial Mayo score, descriptive statistics (number of patients, mean, standard deviation, median, 1st quartile, 3rd quartile, minimum, maximum) will be presented at each visit by dividing the subjects into two groups according to the clinical response at visit 8 (week 56). T-test or Wilcoxon rank sum test will be performed to determine if there is a difference in the mean partial Mayo score depending on the clinical response.

In addition, for the difference in the change of the partial Mayo score at each visit from visit 1 (baseline), the descriptive statistics (number of patients, mean, standard deviation, median, 1st quartile, 3rd quartile, minimum, maximum) will be presented for each group. Paired t-test or Wilcoxon signed rank test will be performed to determine if there is a difference in the change within the group at each visit compared to visit 1 (baseline).

(6) Changes in the full Mayo score at visit 2 (week 8) and visit 8 (week 56) from visit 1 (baseline)

For the full Mayo score, the descriptive statistics (number of patients, mean, standard deviation, median, 1st quartile, 3rd quartile, minimum, maximum) will be presented at visit 1 (baseline), visit 2 (week 8), and visit 8 (week 56) by dividing the subjects into two groups according to the clinical response at visit 8 (week 56). T-test or Wilcoxon rank sum test will be performed to determine if there is a difference in the mean full Mayo score depending on the clinical response.

In addition, for the difference in the change of the full Mayo score at visit 2 (week 8) and visit 8 (week 56) from visit 1 (baseline), the descriptive statistics (number of patients, mean, standard deviation, median, 1st quartile, 3rd quartile, minimum, maximum) will be presented for each group. Paired t-test or

Wilcoxon signed rank test will be performed to determine if there is a difference in the change within the group at each visit compared to visit 1 (baseline).

(7) Changes in the rectal bleeding subscore at visit 2 (week 8) and visit 8 (week 56) from visit 1 (baseline)

For the rectal bleeding subscore, the descriptive statistics (number of patients, mean, standard deviation, median, 1st quartile, 3rd quartile, minimum, maximum) will be presented at visit 1 (baseline), visit 2 (week 8), and visit 8 (week 56) by dividing the subjects into two groups according to the clinical response at visit 2 (week 8) and visit 8 (week 56). T-test or Wilcoxon rank sum test will be performed to determine if there is a difference in the mean rectal bleeding subscore depending on the clinical response.

In addition, for the difference in the change of the rectal bleeding subscore at visit 2 (week 8) and visit 8 (week 56) from visit 1 (baseline), the descriptive statistics (number of patients, mean, standard deviation, median, 1st quartile, 3rd quartile, minimum, maximum) will be presented for each group. Paired t-test or Wilcoxon signed rank test will be performed to determine if there is a difference in the change within the group at each visit compared to visit 1 (baseline).

(8) Mean change in the fecal calprotectin level^a at visit 2 (week 8) and visit 8 (week 56) from visit 1 (baseline)

For the fecal calprotectin level^a, the descriptive statistics (number of patients, mean, standard deviation, median, 1st quartile, 3rd quartile, minimum, maximum) will be presented at each visit for the following subgroups. T-test or Wilcoxon rank sum test will be performed to determine if there is a difference between the groups within each subgroup.

- Depending on the clinical response at visit 2 (week 8)
- Depending on the clinical response at visit 8 (week 56)
- Depending on the clinical remission at visit 2 (week 8)
- Depending on the clinical remission at visit 8 (week 56)
- Depending on the mucosal healing at visit 2 (week 8)
- Depending on the mucosal healing at visit 8 (week 56)

^a Fecal calprotectin level: The below the quantification limit (BQL) value of the fecal calprotectin level is <39.000 mg/kg, and when collected like this, it will be analyzed by replacing it with 39.000 mg/kg, and the total number of replacements will be specified.

| | | Last Update Date |
|----------------------------------|---|------------------|
| dreamcis ATIGERMED COMPANY | CONFIDENTIAL: THIS DOCUMENT AND THE INFORMATION CONTAINED HEREIN ARE PROPRIETARY TO THE COMPANY AND ARE NOT TO BE DISCLOSED. | 02-NOV-2018 |
| | WITHOUT THE WRITTEN PERMISSION OF THE COMPANY. | 02 1.0 . 2010 |
| STATISTICAL ANALYSIS PLAN (V2.0) | | |

(9) Mean change in the hemoglobin level at visit 2 (week 8) and visit 8 (week 56) from visit 1 (baseline)

For the hemoglobin level, the descriptive statistics (number of patients, mean, standard deviation, median, 1st quartile, 3rd quartile, minimum, maximum) will be presented at each visit for the following subgroups. T-test or Wilcoxon rank sum test will be performed to determine if there is a difference between the groups within each subgroup.

- Depending on the clinical response at visit 2 (week 8)
- Depending on the clinical response at visit 8 (week 56)
- Depending on the clinical remission at visit 2 (week 8)
- Depending on the clinical remission at visit 8 (week 56)
- Depending on the mucosal healing at visit 2 (week 8)
- Depending on the mucosal healing at visit 8 (week 56)
- (10) Mean change in the albumin level at visit 2 (week 8) and visit 8 (week 56) from visit 1 (baseline)

For the albumin level, the descriptive statistics (number of patients, mean, standard deviation, median, 1st quartile, 3rd quartile, minimum, maximum) will be presented at each visit for the following subgroups. T-test or Wilcoxon rank sum test will be performed to determine if there is a difference between the groups within each subgroup.

- Depending on the clinical response at visit 2 (week 8)
- Depending on the clinical response at visit 8 (week 56)
- Depending on the clinical remission at visit 2 (week 8)
- Depending on the clinical remission at visit 8 (week 56)
- Depending on the mucosal healing at visit 2 (week 8)
- Depending on the mucosal healing at visit 8 (week 56)
- (11) Mean change in the CRP level at visit 2 (week 8) and visit 8 (week 56) from visit 1 (baseline)

For the CRP level, the descriptive statistics (number of patients, mean, standard deviation, median, 1st quartile, 3rd quartile, minimum, maximum) will be presented at each visit for the following subgroups. T-test or Wilcoxon rank sum test will be performed to determine if there is a difference between the groups within each subgroup.

- Depending on the clinical response at visit 2 (week 8)
- Depending on the clinical response at visit 8 (week 56)

| dreamcis ATIGERMED COMPANY | | Last Update Date |
|------------------------------------|---|------------------|
| | CONFIDENTIAL: | |
| | THIS DOCUMENT AND THE INFORMATION CONTAINED HEREIN ARE PROPRIETARY TO THE COMPANY AND ARE NOT TO BE DISCLOSED | 02-NOV-2018 |
| | WITHOUT THE WRITTEN PERMISSION OF THE COMPANY. | |
| STATISTICAL ANALYSIS DI AN (V) (I) | | |

STATISTICAL ANALYSIS PLAN (V2.0)

- Depending on the clinical remission at visit 2 (week 8)
- Depending on the clinical remission at visit 8 (week 56)
- Depending on the mucosal healing at visit 2 (week 8)
- Depending on the mucosal healing at visit 8 (week 56)

(12) Mean change in the ESR level at visit 2 (week 8) and visit 8 (week 56) from visit 1 (baseline)

For the ESR level, the descriptive statistics (number of patients, mean, standard deviation, median, 1st quartile, 3rd quartile, minimum, maximum) will be presented at each visit for the following subgroups. T-test or Wilcoxon rank sum test will be performed to determine if there is a difference between the groups within each subgroup.

- Depending on the clinical response at visit 2 (week 8)
- · Depending on the clinical response at visit 8 (week 56)
- Depending on the clinical remission at visit 2 (week 8)
- Depending on the clinical remission at visit 8 (week 56)
- Depending on the mucosal healing at visit 2 (week 8)
- Depending on the mucosal healing at visit 8 (week 56)

(13) Changes in the fecal microbial composition

The analysis of the change in the fecal microbial composition will be conducted separately at the Department of Microbiology of Chung-Ang University.

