**Secondary Endpoint:**

- The percentage of patients with clinical remission at week 8 and 56 (in week 8 responders)

*Clinical remission is defined as a total Mayo score  $< 2$  points, with no individual sub-score exceeding 1 point*

- The percentage of patients with steroid-free remission at week 8 and 56 (in week 8 responders).

*Steroid free remission is defined as patients who are in remission without the use of systemic steroids within the past 12 weeks prior to assessment.*

- The percentage of patients with mucosal healing at week 8 and 56 (in week 8 responders).

*Mucosal healing is defined as an endoscopy sub-score of 0 or 1. Endoscopic findings were scored on a scale from 0 to 3 as follows:*

*0 = Normal or inactive disease; 1 = Mild disease (erythema, decreased vascular pattern, mild friability); 2 = Moderate disease (marked erythema, lack of vascular pattern, friability, erosions); 3 = Severe disease (spontaneous bleeding, ulceration).*

- The change of partial Mayo score from baseline overtime

- The change of the composition of Fecal micro biota from baseline at week 56

- The mean change of Fecal calprotectin level from baseline at week 56

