**Week 16, 24, 32, 40 and 48 after baseline**

- 1) Partial Mayo score

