5.1 Effectiveness Assessment

The subjects participating in this study will be followed up at weeks 8, 16, 24, 32, 40, 48, and 56 according to the clinical procedure after enrollment. (The window period of each follow-up is ± 1 week.) At baseline, demographic, disease, and drug-related data will be collected. Additionally, the Mayo score will be measured along with the routine laboratory tests.

For the enrolled subjects, 160 mg will be administered at the time of enrollment, 80 mg 2 weeks after the first dose, and 40 mg biweekly thereafter, according to the Korean authorization details. At week 8, the clinical

| dreamcis ATIGERMED COMPANY | | Last Update Date |
|----------------------------------|--|------------------|
| | CONFIDENTIAL: | |
| | THIS DOCUMENT AND THE INFORMATION CONTAINED HEREIN ARE | 02-NOV-2018 |
| | PROPRIETARY TO THE COMPANY AND ARE NOT TO BE DISCLOSED | 02-INO V-2018 |
| | WITHOUT THE WRITTEN PERMISSION OF THE COMPANY. | |
| STATISTICAL ANALYSIS PLAN (V2.0) | | |

response will be assessed. At this time, the subjects with a clinical response will be able to continue adalimumab treatment according to the Korean insurance coverage standards, and will be followed up through this study.

The clinical response is defined as 3 points or more reduction and 30% or more reduction in the full Mayo score (endoscopic findings, stool frequency, rectal bleeding, physician's global assessment) at week 8 from the baseline plus 1 point or more reduction in the rectal bleeding subscore or an absolute rectal bleeding subscore of 1 point or less.

At every follow-up visit, the partial Mayo score (stool frequency, rectal bleeding, physician's global assessment) will be measured to observe the effect of adalimumab, and routine laboratory tests will be conducted according to the routine treatment procedures.

At baseline, week 8, week 56, and when there is an inadequate response, the full Mayo score will be measured with endoscopy, which will also be conducted according to the routine treatment procedures.

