The frequency and percentage of subjects who showed a clinical response at visit 2 (week 8) will be presented by classifying the subjects into two groups depending on the TNF antagonist naivety, and the 95% confidence interval for the result will be calculated. Additionally, the frequency and percentage of subjects who showed a persistent clinical response at visit 2 (week 8), visit 4 (week 24), and visit 8 (week 56) will be presented for each group, and the 95% confidence interval for the result will be calculated. Chi-square test or Fisher's exact test will be performed to determine if there is a difference in the clinical response rate between the two groups.

(5) Clinical remission at each visit depending on the TNF antagonist naivety

The frequency and percentage of subjects who showed clinical remission at visit 2 (week 8) will be presented by classifying the subjects into two groups depending on the TNF antagonist naivety. Among the subjects who showed a clinical response at visit 2 (week 8), the frequency and percentage of those who showed clinical remission at visit 4 (week 24) and visit 8 (week 56) will also be presented for each group. Chi-square test or Fisher's exact test will be performed to check if there is a difference in the clinical remission rate between the two groups.

(6) Clinical response without steroid administration at each visit depending on the TNF antagonist naivety

The frequency and percentage of subjects who showed a clinical response without steroid administration at visit 2 (week 8) will be presented by classifying the subjects into two groups depending on the TNF antagonist naivety. Among the subjects who showed a clinical response at visit 2 (week 8), the frequency and percentage of those who showed a clinical response without steroid administration at visit 4 (week 24) and visit 8 (week 56) will also be presented for each group. Chi-square test or Fisher's exact test will be performed to determine if there is a difference in the clinical response rate without steroid

| | | Last Update Date |
|----------------------------------|---|------------------|
| dreamcis ATIGERMED COMPANY | CONFIDENTIAL: THIS DOCUMENT AND THE INFORMATION CONTAINED HEREIN ARE PROPRIETARY TO THE COMPANY AND ARE NOT TO BE DISCLOSED. | 02-NOV-2018 |
| | WITHOUT THE WRITTEN PERMISSION OF THE COMPANY. | 02 1.0 . 2010 |
| STATISTICAL ANALYSIS PLAN (V2.0) | | |

administration between the two groups.

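### Week-24 clinical remission keeps the 2-point limit but drops endoscopy, so its rate is tilted upward and cannot be compared with the week-8 and week-56 rates under the same label

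*SAP*

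**What the plan says.** SAP 6.3.2(1), footnote c, gives two rules under one name. At weeks 8 and 56, clinical remission is "Defined as the case of full Mayo score ≤2 points and each subscore ≤1 point". For the middle visit the footnote continues: "For visit 4 (week 24), however, it is defined as the case of partial Mayo score ≤2 points and each subscore ≤1 point".

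SAP 5.1 shows that the two scores share stool frequency, rectal bleeding and the physician's global assessment. Only the full score adds endoscopy. The protocol's visit list in section 9.3, under "Week 16, 24, 32, 40 and 48 after baseline", schedules the partial score alone, so the full rule cannot be applied at week 24.

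Item (1) reports week 8 without restriction to responders, then weeks 24 and 56 together among week-8 responders. Three other places inherit the split definition:

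- 6.3.2(3), which tabulates "the frequency and percentage of those who showed clinical remission without steroid administration" at the same visits;
- 6.5(5), remission by TNF antagonist naivety;
- 6.5(7), steroid-free remission by TNF antagonist naivety.

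SAP 4.1.2 lists remission at weeks 8 and 56 only, and SAP 4.1 describes week 24 as an interim analysis to be done if needed. Sections 6.3.2 and 6.5 nevertheless tabulate week 24 without condition.

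**The concern.** An item was removed and the limit on the sum stayed at 2. A patient with a partial score of 2 and endoscopy 1 has a full score of 3. That patient is in remission by the week-24 rule and not by the week-56 rule, with nothing changed. A patient with a low partial score and endoscopy 2 or 3 also counts at week 24.

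The SAP does adjust the threshold elsewhere. In 6.3.1 the required fall for response drops from 3 points on the full score to 2 points on the partial score at week 24. Remission gets no such adjustment.

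What is at stake is how the table is read. Weeks 24 and 56 stand side by side for the same week-8 responders, and a lower week-56 figure invites the conclusion that remission was lost.

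**Working it through.** **Inputs.** The two rules are from SAP 6.3.2, footnote c, and the items in each score from SAP 5.1. The endoscopy range is from the protocol's Secondary Endpoint text: "Endoscopic findings were scored on a scale from 0 to 3 as follows". The ranges of the other three items do not matter, because both rules require them to be 0 or 1. The documents state no expected remission rate and no endoscopy distribution, so there is no planned figure to reproduce.

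**Step 1: which profiles qualify.**

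- Week-24 rule: three items, each 0 or 1, sum at most 2, gives 1 + 3 + 3 = 7 partial profiles. Endoscopy is free over four levels: 7 × 4 = 28.
- Full rule: four items, each 0 or 1, sum at most 2, gives 1 + 4 + 6 = 11.
- All 11 lie inside the 28, because removing a non-negative item cannot raise the sum.
- The other 28 − 11 = 17 count only at week 24: 7 × 2 = 14 with endoscopy 2 or 3, and 3 with partial score 2 and endoscopy 1.
- The extreme case is partial score 2 with endoscopy 3, a full score of 5.

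These are counts of profiles, not of patients. They establish direction, not size.

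**Step 2: illustrative size with unchanged disease.** Let q be the share of week-8 responders who meet the partial rule, s the share of those with partial score 0 or 1, and e0 and e1 their shares with endoscopy 0 and 1. Endoscopy is taken as distributed alike at each partial score. All of these values are assumptions.

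Full-rule rate = q × [s × (e0 + e1) + (1 − s) × e0]; week-24 rate = q.

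| q | s | Endoscopy 0 / 1 / ≥2 | Full-rule rate | Week-24 rate | Gap (points) |
|---|---|---|---|---|---|
| 50% | 80% | 50/40/10% | 0.5 × (0.72 + 0.10) = 41% | 50% | 9 |
| 50% | 60% | 40/40/20% | 0.5 × (0.48 + 0.16) = 32% | 50% | 18 |
| 70% | 60% | 30/40/30% | 0.7 × (0.42 + 0.12) = 37.8% | 70% | 32.2 |

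The first and last rows are the extremes for q from 50 to 70%, s from 60 to 80%, and endoscopy from 30/40/30% to 50/40/10%. The gap is zero only if every partial-rule remitter has endoscopy 0, or endoscopy 1 with a partial score of at most 1.

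**Step 3: the denominator at week 8.** Entry requires a Mayo score of at least 6. A full-rule remitter has at most 2, so has fallen by at least 4 points and at least 1 − 2/6 = 67%, with rectal bleeding at most 1. Every week-8 remitter is therefore a responder. Moving from all subjects to responders leaves the numerator unchanged and multiplies the rate by 1/0.75 = 1.33, using the 75% response rate assumed for the sample size (a week-12 figure).

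In the middle row, 32% among responders is 32% × 0.75 = 24% of all subjects. With no change in disease, the SAP's table would read 24%, 50% and 32%. Of the 26-point rise to week 24, 32 − 24 = 8 points come from the denominator and 50 − 32 = 18 from the rule.

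**The case against.** The week-24 definition is stated openly, and with no endoscopy scheduled some partial-score rule is unavoidable. Week 24 is not a listed remission endpoint, and no test, model or plot of remission across visits is planned. The SAP already follows the partial Mayo score over time in 6.3.2(5). All of this is correct and limits the importance of the point. But the footnote does not say that the rates are not comparable. Item 6.3.2(5) summarises scores by week-56 response and gives no remission proportion. Nowhere is one remission rule applied at all three visits.

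Three stronger readings are tempting, and the documents do not support them.

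- **That the tables will show a rise and then a fall.** The definition sets a direction of bias, not the observed curve. True change could hide it, and so could exclusions at week 56. Subjects who stop adalimumab leave the study, 6.3.2 excludes those with uncollected Mayo items, and 6.6 carries partial items forward but not endoscopy. In the middle row above, excluding 40% of responders at week 56, all non-remitters, gives 0.32/0.60 = 53%, above the week-24 figure of 50%.
- **That the rise from week 8 to week 24 measures the effect of the cut-off.** Part of it is the change of denominator.
- **That the TNF-naivety tests are biased.** At any one visit both groups face the same rule, so the change of rule across visits does not by itself create a difference between groups. Only reading across visits is affected.

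**Conclusion.** The point holds as one of comparability across visits. That the week-24 rule can never be harder than the full rule follows from the definitions and needs no assumption about patients. A decline in remission from week 24 to week 56 among week-8 responders could reflect the definition alone. The comparison of week 8 with week 24 is distorted in the same direction twice, by the rule and by the denominator.

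The size cannot be derived from the documents. The range of 9 to 32 points rests wholly on the assumed shares above, and no single inflation factor should be quoted. The issue touches 6.3.2(1), 6.3.2(3), 6.5(5) and 6.5(7) when they are read across visits. The week-8 and week-56 results share one rule and are not called into question here.

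**What to change.** In SAP 6.3.2(1), 6.3.2(3), 6.5(5) and 6.5(7):

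1. Reserve *clinical remission* for the full-Mayo rule at weeks 8 and 56.
2. Label the week-24 result *partial Mayo remission*.
3. Add a row applying that same partial-score rule at weeks 8, 24 and 56, with week-8 responders as the denominator at all three visits.
4. Name one missing-data rule for that row and use it at every visit. Sections 6.3.2 (exclusion) and 6.6 (carrying partial items forward) currently differ.
5. Describe any change over time in remission that involves week 24 from that row only.

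The cost is SAP wording and one extra table row. The three partial-score items are already scheduled at weeks 8, 24 and 56, so no new data are needed. In the middle row of the working, unchanged disease would then read 50%, 50% and 50%.

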## **9.8 Quality Control**

Prior to the initiation of the study, an investigator's meeting or initiation visit will be held with AbbVie personnel or his/her designee, the investigators and their study coordinators. This meeting will include a review of the protocol and CRF completion guideline.

Investigator must assure that the study is conducted in accordance with the protocol and all relevant regulations and CRF is completed accurately.

In general, monitoring for any site is not required, but, for quality assurance, internal consistency check for completeness and consistency of data will be done to ensure the integrity of the information reported.

CRF will be reviewed by CRAs at AbbVie or their designees for completeness and conclusiveness and when necessary, query will be generated and will be resolved by the site staffs.

All data hand-entered in the database will be verified by a double-key entry procedure. Any discrepancies will be reviewed against the hard copy CRF and corrected. After completion of the entry process, computer logic checks will be run. Any necessary corrections will be made to the database and documented.

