2.3.2 Inclusion Criteria

- (1) Subject must be an adult \geq 19 years
- (2) Subject with active moderate-to-severe ulcerative colitis patients with Mayo score of ≥ 6 points and endoscopic sub-score of ≥ 2 points despite treatment with corticosteroids and/or immunosuppressants.
- (3) Subject who must have tuberculosis (TB) Screening Assessment in accordance with Korean reimbursement guideline
- (4) Subjects who are started on adalimumab treatment in normal clinical practice setting by their physician.
- (5) Subject must provide written authorization form to use personal and/or health data prior to the entry into the study

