(7) Clinical remission without steroid administration at each visit depending on the TNF antagonist naivety

The frequency and percentage of subjects who showed clinical remission without steroid administration at visit 2 (week 8) will be presented by classifying the subjects into two groups depending on the TNF antagonist naivety. Among the subjects who showed a clinical response at visit 2 (week 8), the frequency and percentage of those who showed clinical remission without steroid administration at visit 4 (week 24) and visit 8 (week 56) will also be presented for each group. Chi-square test or Fisher's exact test will be performed to determine if there is a difference in the clinical remission rate without steroid administration between the two groups.

(8) Mucosal healing at each visit depending on the TNF antagonist naivety

The frequency and percentage of subjects who showed mucosal healing at visit 2 (week 8) will be presented by classifying the subjects into two groups depending on the TNF antagonist naivety. Among the subjects who showed a clinical response at visit 2 (week 8), the frequency and percentage of those who showed mucosal healing at visit 8 (week 56) will also be presented for each group. Chi-square test or Fisher's exact test will be performed to determine if there is a difference in the mucosal healing rate between the two groups.

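### Baseline endoscopic grade decides whether a subject must improve one grade or two to count as healed, but the SAP leaves it out of the healing table and the TNF-naivety test and brings it into the predictor models only indirectly.

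*SAP*

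**What the plan says.** Protocol and SAP agree on the endpoint. Protocol 9.1 states "Mucosal healing is defined as an endoscopy sub-score of 0 or 1", and SAP 6.3.2(4), footnote e, has "Mucosal healing: Defined as the case of an endoscopy subscore of 0 or 1 in the full Mayo score". Eligibility (SAP 2.3.2) requires "endoscopic sub-score of ≥ 2 points despite treatment with corticosteroids and/or immunosuppressants". On the 0 to 3 scale, every eligible subject therefore starts at 2 or 3.

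SAP 6.3.2(4) reports healing as a frequency and percentage: at week 8, and at week 56 among week-8 responders. It does not split the result by entry grade.

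SAP 6.5(8) compares healing between TNF-naive and experienced subjects: "Chi-square test or Fisher's exact test will be performed to determine if there is a difference in the mucosal healing rate between the two groups". No stratification or adjustment is mentioned.

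SAP 6.5(1) names mucosal healing as an outcome of the logistic regressions. Each factor is first tested alone, and the significant ones go into a multiple model. Full Mayo score is on the candidate list; the endoscopic sub-score by itself is not. The SAP allows variables to be added or removed in the light of the data.

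The baseline endoscopic sub-score is collected for every subject (Protocol 9.3, Baseline). SAP 6.2 summarises the baseline full Mayo score and names its endoscopic component.

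**The concern.** Identifying predictive factors is one of the study's two objectives. For healing, the distance a subject must travel is set at entry: one grade or two. A baseline value of that kind would be expected to be prognostic. If it is left out, two things follow.

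- **Confounding.** If TNF-naive subjects enter at grade 2 more often than experienced subjects, their crude healing rate will be higher even when prior exposure has no effect. The same holds for any other candidate predictor associated with entry grade.
- **Lost precision.** A prognostic covariate left out of a logistic model costs power for the predictors that do matter.

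Total Mayo score is a weak stand-in. The same total can arise with an endoscopic sub-score of 2 or 3, and the univariate screen may drop it.

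**Working it through.** **Plan's own figures.** The documents state no rate, precision or power for mucosal healing. The only design figure is the study size of 147. An exact (Clopper-Pearson) 95% interval of full width 0.15 at a rate of 75% needs 139 subjects, and 139/0.95 = 146.3, rounded up to 147. The figure reproduces and this point does not affect it. I use n = 139 as the evaluable number at week 8.

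**Inputs that have to be assumed.** The documents do not give the share of subjects entering at grade 2, healing by entry grade, or the split by TNF naivety. I take:
- grade-2 share: 60% of naive and 40% of experienced subjects
- true healing: 60% from grade 2 and 35% from grade 3, identical in naive and experienced subjects
- group sizes: 70 and 69

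**Step 1: apparent naivety difference with no naivety effect.**
- Naive: 0.60 × 0.60 + 0.40 × 0.35 = 0.36 + 0.14 = 0.50
- Experienced: 0.40 × 0.60 + 0.60 × 0.35 = 0.24 + 0.21 = 0.45
- Difference: 5 points, which equals the share imbalance times the healing gap, 0.20 × 0.25

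**Step 2: rejection rate of the crude test.**
- Standard error: √(0.50 × 0.50/70 + 0.45 × 0.55/69) = 0.0846
- Standardised difference: 0.05/0.0846 = 0.59
- Two-sided rejection at 1.96: P(Z > 1.37) + P(Z < −2.55) = 0.086 + 0.005 = about 9%

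Simulation of the uncorrected chi-square test (200,000 trials) gives 9.0%. The Cochran-Mantel-Haenszel test stratified by entry grade, on the same data, gives 5.0%.

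**Step 3: range over the assumed imbalance** (healing rates as above).

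| Grade-2 share, naive v experienced | Apparent difference | Crude rejection | Stratified rejection |
|---|---|---|---|
| 50% v 50% | 0 points | 4.8% | 5.0% |
| 55% v 45% | 2.5 points | 5.8% | 5.0% |
| 60% v 40% | 5 points | 9.0% | 5.0% |
| 70% v 30% | 10 points | 21.7% | 5.0% |

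The problem vanishes if entry grade is balanced and grows quickly if it is not.

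**Step 4: power for another predictor.** Assume that entry grade shifts the log-odds of healing by 1.5 and that the predictor of interest has a log odds ratio of 0.5 per SD, with n = 139. Adding entry grade to the logistic model raises simulated power from about 69% to about 74%. The exact levels depend on the assumed intercept; the gain is about 5 to 6 points.

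**Week 56.** Only week-8 responders count. At the planning rate of 75% that is about 0.75 × 139 = 104 subjects, so some strata may be small.

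**The case against.** The case against has several sound parts.

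- **The definition is not at fault.** Healing is an absolute state, as clinical remission is. Adjacent cut-offs mean that no eligible subject already meets the endpoint at entry. The lack of a minimum change, which clinical response has, is not a defect. This stands.
- **Entry severity is not wholly ignored.** Baseline full Mayo is summarised, it is a candidate predictor, and the SAP lets variables be added. This stands as far as it goes. But the total does not separate grade 2 from grade 3, discretion to add a variable is not prespecification, and the naivety test has no adjustment.
- **The effect is modest and the analyses are exploratory.** This is fair. A 5-point artefact needs a 20-point imbalance and a 25-point healing gap, both assumed.

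A reader might go further and infer that misreading inflates the healing rate. The grade wording is qualitative ("1 = Mild disease (erythema, decreased vascular pattern, mild friability); 2 = Moderate disease (marked erythema, lack of vascular pattern, friability, erosions"), no second or central reader is described, and the protocol says "In general, monitoring for any site is not required". The documents do not support that inference. They give no reader agreement, and error also hides true healing. Let h be true healing, g the share of non-healed subjects at grade 2, s the share of healed subjects at grade 1, and m the misreading rate in each direction. The net shift is (1 − h)gm − hsm. At h = 0.3, g = 0.7, s = 0.5, m = 0.2 it is 0.098 − 0.030 = about +7 points. At h = 0.5, g = 0.3, s = 0.7, m = 0.2 it is 0.030 − 0.070 = −4 points. Neither size nor direction is fixed. At week 56, moreover, a one-grade misreading cannot by itself bring a subject into the denominator, because a week-8 clinical response needs a drop of at least 3 points and 30% in full Mayo.

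**Conclusion.** The point holds as a near-costless improvement to the analysis. It is neither an error in the endpoint nor a contradiction between the documents. Entry grade sets the improvement required, is already recorded, and is left out of the healing table and the naivety test; the predictor models carry it only through total Mayo. Any factor associated with entry grade can therefore appear to predict healing.

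Under the stated assumptions the crude naivety comparison shows 5 points with no naivety effect and rejects about 9% of the time, against about 5% when stratified. The true size depends on a grade imbalance that the documents do not give and could be nil. Two stronger conclusions should not be drawn: that the 0/1 threshold is wrong, or that the reported healing rate is biased upward by reading error. The study size and the primary endpoint are unaffected.

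**What to change.** Keep the 0/1 definition and change three places in the SAP.

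1. **SAP 6.5(1):** include the baseline endoscopic sub-score (2 v 3) as a fixed covariate in every mucosal-healing model, outside the univariate screen. If total Mayo also stays in, its coefficient then reflects the remaining components.
2. **SAP 6.5(8):** test the naivety difference with a Cochran-Mantel-Haenszel test stratified by baseline endoscopic sub-score, using the exact version if strata are sparse. Keep the crude rates as description.
3. **SAP 6.3.2(4):** as supporting description, add a shift table of endoscopic sub-score by entry grade, at week 8 for all subjects and at week 56 for week-8 responders.

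The cost is SAP wording, one table and one model degree of freedom. No new data, visits or subjects are needed. These changes do not address the reliability of the endoscopic readings.
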